Fasting Visit ^d			X				X				X		X		X	X	X		X	X	X
Telephone Visit				X		X		X		X		X		X							
Laboratory Tests																					
Serum pregnancy test ⁿ	X																				
Urine pregnancy test ^o			X										X				X		X		
Follicle-stimulating hormone test ^p	X																				
Chemistry panel	X ^q												X				X		X	X	X
Fasting serum glucose			X				X				X		X		X	X	X		X	X	X
Lipid panel			X																X	X	X
Urinary albumin/creatinine ratio	X ^q																		X	X	X
Serum creatinine, eGFR (CKD-EPI) ^r	X ^q												X				X		X	X	
Calcitonin	X ^q												X				X		X	X	X
Hematology	X ^q												X				X		X	X	X
HbA1c	X		X				X				X		X		X	X	X		X	X	X
Pancreatic amylase, lipase	X ^q												X				X		X	X	X
Immunogenicity ^s			X				X						X				X		X	X	X
PK sample for Immunogenicity ^t			X				X						X				X		X	X	X

	Study Period I		Study Period II																	Study Period III	
	Screening Lead in		Treatment Period																	Safety F/U	
Visit	1	2	3 ^a	4	5	6	7	8	9	10	11	12	13	14	15	16	17	18	19	ET ^b	801
Week of Treatment	-3	-2	0	1	2	3	4	5	6	7	8	10	12	14	16	20	24	32	40		4 weeks Post End of Tx
Allowable Deviation (days) ^c	-	±3	±7	±3	±3	±3	±3	±3	±3	±3	±3	±3	±3	±3	±3	±3	±3	±7	±7		±7
Fasting Visit ^d			X				X				X		X		X	X	X		X	X	X
Telephone Visit				X		X		X		X		X		X							
Anti-GAD antibody			X																		
Patient Reported Outcomes ^e																					
APPADL			X																X	X	
EQ-5D-5L			X																X	X	
IW-SP			X																X	X	
DTSQs			X																		
DTSQc																			X	X	

Abbreviations: APPADL = Ability to Perform Physical Activities of Daily Living; BG = blood glucose; BP = blood pressure; CKD-EPI = Chronic Kidney Disease-Epidemiology; DTSQc = Diabetes Treatment Satisfaction Questionnaire change; DTSQs = Diabetes Treatment Satisfaction Questionnaire status; eGFR = estimated glomerular filtration rate; EQ-5D-5L = European Quality of Life- dimensions; ET = early termination; F/U = follow-up; GAD = glutamic acid decarboxylase; HbA1c = hemoglobin A1c; PR = pulse rate; IW-SP = Impact of Weight on Self Perception; PK = pharmacokinetics; SMBG = self-monitored blood glucose; TTT = treat to target; Tx = treatment.

- ^a Baseline assessments must be completed before processing in the interactive web-response system.

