- ^p Follicle-stimulating hormone test performed at Visit 1 for potential postmenopausal women age 45 years or above with an intact uterus, not on hormone therapy or oral contraceptives, and who have had spontaneous amenorrhea for more than 6 months and less than 12 months and estradiol levels consistent with a postmenopausal state (FSH \geq 40 mIU/mL and estradiol <30 pg/mL).
- ^q Screening visit assessment will serve as baseline.
- ^r The CKD-EPI equation will be used by the central lab to estimate and report eGFR.
- ^s In the event of systemic drug hypersensitivity reactions (immediate or nonimmediate), additional blood samples will be collected including ADA, PK, and an exploratory immune safety sample.
- ^t PK samples for immunogenicity must be taken prior to drug administration.
- ^u All PROs should be completed before any other study procedures if the patient is not adversely affected by the fasting condition or completed after the patient has sufficiently recovered from the preceding visit procedures.

Note: Patients will be encouraged to collect a daily fasting BG and a weekly 4-point SMBG. Missing a fasting BG measurement will not be considered a protocol deviation.

3. Introduction

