6.2. General Considerations

Statistical analysis of this study will be the responsibility of Eli Lilly and Company (Lilly) or its designee. All statistical analyses will be conducted with SAS Version 9.4 or higher unless otherwise stated. Any change to the data analysis methods described in the protocol will require an amendment only if it changes a principal feature of the protocol. Any other changes to the data analysis methods described in the protocol, and the justification for making the change, will be described in the SAP or the clinical study report (CSR). Some analyses and summaries described in this analysis plan may not be conducted if not warranted by data (e.g., few events to justify conducting an analysis). Listings of events will be provided in such situations.

Additional analyses of the data may be conducted as deemed appropriate without further changes made to the protocol or SAP, even after the primary or final database locks (DBL).

Patients inadvertently receiving incorrect study treatment are expected to switch to their randomized treatment arm as soon as possible. Patients assigned to tirzepatide may not be able to tolerate the maximum dose of the randomized treatment arm and may continue study participation on a reduced maintenance dose. Continuing on a reduced maintenance dose will neither be considered as discontinuation of randomized treatment nor will be considered as non-

compliant to randomized treatment. Additionally, to avoid potential selection biases, unless stated otherwise, statistical summaries and analyses will be conducted based on randomized maintenance dose regardless of the actual treatment received by the patient.

Last available measurement during Visit 1 to Visit 3 (including unscheduled visits) prior to or on the first dose day will serve as baseline. Immunogenicity, urinary albumin to creatinine ratio, lipid values, and health outcome measures obtained at Visit 3, regardless of the timing relative to first dose, will be used as baseline.

Efficacy and safety will be assessed using the modified intent-to-treat (mITT) population, which consists of all randomly assigned participants who are exposed to at least one dose of study drug. The primary and multiplicity adjusted objectives, will be performed on EAS and FAS. When change from baseline is included as a response variable of analysis models, the patient will be included in the analysis only if he/she has a baseline and a postbaseline measurement.

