6.13.2.12.3. Liver Enzymes

Analyses for laboratory analyte measurements are described in [Section 6.16](#). This section describes additional analyses of liver enzymes. In addition, the following will be provided by treatment group:

- Shift table of maximum to maximum alanine aminotransferase (ALT) measurement from baseline to postbaseline with the following categories: \leq ULN, >1 to $<3 \times$ ULN, ≥ 3 to $<5 \times$ ULN, ≥ 5 to $<10 \times$ ULN, $\geq 10 \times$ ULN.
- Shift table of maximum to maximum aspartate transaminase (AST) measurement from baseline to postbaseline with the following categories: \leq ULN, >1 to $<3 \times$ ULN, ≥ 3 to $<5 \times$ ULN, ≥ 5 to $<10 \times$ ULN, $\geq 10 \times$ ULN.
- Shift tables of maximum to maximum total bilirubin and direct bilirubin from baseline to postbaseline with the following categories: \leq ULN, >1 to $<2 \times$ ULN, $\geq 2 \times$ ULN.
- Shift tables of serum alkaline phosphatase (ALP) from baseline to postbaseline with the following categories: \leq ULN, >1 to $<2 \times$ ULN, $\geq 2 \times$ ULN.

Maximum baseline will be the maximum non-missing observation in the baseline period. The maximum value will be the maximum non-missing value from the postbaseline period. Planned and unplanned measurements will be included.

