6.13.2.14. Acute Renal Events

Laboratory measures related to renal safety will be analyzed as specified for laboratory measurements in Section 6.16.

Two shift tables examining renal function will be created. A min-to-min shift table of estimated glomerular filtration rate (eGFR) estimated by the Chronic Kidney Disease Epidemiology Collaboration (CKD-EPI) equation with unit ml/min/1.73m², using categories (<30, ≥ 30-to 45, ≥45- to <60, ≥60 to <90, and ≥90 mL/min/1.73m²). A max-to-max shift table of urine albumin-to-creatinine ratio (UACR), using the categories UACR<30 mg/g, 30 mg/g ≤UACR≤300 mg/g, UACR>300 mg/g (respectively, these represent normal, microalbuminuria, and macroalbuminuria).

The AE database will be searched using SMQs of acute renal failure and chronic kidney disease to identify events consistent with acute renal events. The incidence of the resulting TEAEs will be summarized by treatment and PT. Detailed searching criteria can be found in [Appendix 1](#). Severe/serious acute renal events will be considered AESIs.

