6.16. Clinical Laboratory Evaluation

All laboratory data will be reported in the International System of Units. Selected laboratory measures will also be reported using conventional units. Values that are outside of reference ranges will be flagged as high (H) or low (L) in the listings. Descriptive summaries by treatment

and by nominal visit will be provided for the baseline and postbaseline values as well as the change from baseline values.

Observed and change from baseline values for each visit will be displayed in box plots for patients who have both a baseline and a postbaseline planned measurement. Unplanned measurements will be excluded from box plots.

A shift table will be provided including unplanned measurements. The shift table will include the number and percentage of patients within each baseline category (low, normal, high, or missing) versus each postbaseline category (low, normal, high, or missing) by treatment. The proportion of patients shifted will be compared between treatments using Fisher's exact test.

For qualitative laboratory analytes, the number and percentage of patients with normal and abnormal values will be summarized by treatment.

A listing of abnormal findings will be created for laboratory analyte measurements, including qualitative measures. The listing will include patient ID, treatment group, laboratory collection date, study day, analyte name, and analyte finding.

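### SAP 6.2 takes the UACR baseline from Visit 3, but the protocol schedules no UACR at Visit 3 and makes the screening value the baseline

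*SAP*

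**What the plan says.** SAP 6.2 (General Considerations) defines baseline in two consecutive sentences. The first is general: "Last available measurement during Visit 1 to Visit 3 (including unscheduled visits) prior to or on the first dose day will serve as baseline". The second names four groups of measures for which the Visit 3 value is used: immunogenicity, followed by "urinary albumin to creatinine ratio, lipid values, and health outcome measures obtained at Visit 3, regardless of the timing relative to first dose".

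The protocol treats UACR differently. In Table GPHO.1 (Section 2), the row "Urinary albumin/creatinine ratio" is marked at Visit 1, Visit 19, early termination (ET) and Visit 801. The Visit 3 cell is empty. The Visit 1 mark carries footnote q: "Screening visit assessment will serve as baseline".

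Two parts of the SAP need a UACR baseline. Section 6.13.2.14 plans a maximum-to-maximum UACR shift table with cut-points at 30 and 300 mg/g. It also sends renal laboratory data to the general laboratory section: "Laboratory measures related to renal safety will be analyzed as specified for laboratory measurements in Section 6.16". Section 6.16 then requires descriptive summaries by treatment "and by nominal visit will be provided for the baseline and postbaseline values as well as the change from baseline values".

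**The concern.** The two documents name different visits as the source of the UACR baseline, and the visit named in the SAP has no scheduled UACR sample. A program that follows the SAP sentence as written finds no scheduled baseline for any patient.

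This could go unnoticed. The laboratory shift table in SAP 6.16 has a category for missing baseline, and its box plots are limited to patients with both a baseline and a postbaseline value. Such a program could run without error, place patients in the missing category and leave the plots empty.

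There is also a smaller risk. If an unscheduled UACR were taken at Visit 3, even after the first dose, the SAP sentence would make it the baseline in place of the screening value that the protocol designates.

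**Working it through.** No calculation applies. The check sets the schedule beside the two baseline rules.

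**Step 1. Are the measures in the SAP's Visit 3 sentence scheduled at Visit 3?** From Table GPHO.1 (21 columns: Visits 1 to 19, ET and 801):

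| Measure group | Scheduled at | At Visit 3? |
|---|---|---|
| Immunogenicity | 3, 7, 13, 17, 19, ET, 801 | Yes |
| Lipid panel | 3, 19, ET, 801 | Yes |
| Health outcomes: APPADL, EQ-5D-5L, IW-SP | 3, 19, ET | Yes |
| Health outcomes: DTSQs | 3 | Yes |
| UACR | 1, 19, ET, 801 | **No** |

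Three of the four groups fit the sentence and UACR does not. UACR is marked in 4 of the 21 columns, and only one of these, Visit 1, comes before treatment.

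**Step 2. How does the SAP treat the other tests that take baseline from screening?** Six laboratory rows carry footnote q: chemistry, UACR, serum creatinine/eGFR, calcitonin, hematology, and pancreatic amylase/lipase. All six are marked at Visit 1 and none at Visit 3. Five are left under the general rule in SAP 6.2, which picks up the Visit 1 value. UACR is the only one named in the Visit 3 sentence (6 − 5 = 1).

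**Step 3. Was the change deliberate?** Both documents require changes to the protocol's analysis methods to be described and justified in the SAP or study report. The SAP revision history does not mention a UACR baseline, and the protocol amendment summary adds no Visit 3 UACR sample. Protocol 5.1 says in general terms that baseline laboratory measures are collected at Visit 3. It does not name UACR, and it cannot override a schedule that gives six rows a screening baseline.

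**Step 4. What does each reading produce?**

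| Reading | UACR baseline from scheduled samples |
|---|---|
| SAP Visit 3 sentence, literally | None |
| SAP general rule | Visit 1 |
| Protocol footnote q | Visit 1 |

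**Step 5. Which outputs are affected?** The UACR shift table, one of the two renal shift tables in SAP 6.13.2.14, and the UACR summaries under SAP 6.16. The eGFR shift table, the renal adverse-event searches and the primary and key secondary analyses do not use this baseline.

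**The case against.** The best defense is that the second sentence of the SAP rule only relaxes the before-dosing condition for samples taken at Visit 3. It does not say that earlier values are to be ignored. With no Visit 3 UACR, it has nothing to act on, and the general rule immediately before it supplies the Visit 1 value. Footnote q gives the same answer. Since Visit 1 is the only scheduled sample before dosing, a sensible programmer would reach the right value.

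This reading is reasonable and is probably what would happen. It limits the harm but does not remove the error. The SAP states no fallback, and on this reading UACR has no reason to be in the sentence at all.

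A second argument is that a maximum-to-maximum table uses the highest value in the baseline period, so the Visit 3 sentence may not govern it. The SAP does define this for liver enzymes in 6.13.2.12.3 ("Maximum baseline will be the maximum non-missing observation in the baseline period"), but it does not extend the definition to UACR. Even if it did, the change-from-baseline summaries in 6.16 would still depend on SAP 6.2.

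The point about importance stands. UACR is not named in any study objective, and the counts above show the mismatch without measuring an effect on any result.

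**Conclusion.** The SAP sentence is wrong as written, and its impact is low. It contradicts the protocol on the source of the UACR baseline and, taken literally, leaves no patient with a scheduled value. The effect is confined to UACR safety outputs. No data are lost, because the Visit 1 sample is scheduled whichever rule is used.

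The conclusion rests on the schedule and footnote q as printed and on there being no separate instruction to collect UACR at Visit 3; neither document contains one. The documents do not state how complete the Visit 1 UACR values are.

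**What to change.** Delete UACR from the Visit 3 sentence in SAP 6.2. It then falls under the general rule with the other five footnote-q tests, and its baseline is the Visit 1 value.

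One small difference from the protocol remains. The general rule would prefer a later unscheduled sample taken before dosing, whereas footnote q fixes the screening value. That applies equally to all six tests and is not specific to UACR. With one scheduled sample before dosing, the latest and the highest baseline values coincide, so the deletion normally settles the shift table as well.

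The cost is one phrase in the SAP, with no change to data collection or trial conduct. It should be made before database lock.

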Safety assessment will be based on all available data including 4-week safety follow up period, irrespective of whether they were obtained while the participants had discontinued the study drug or whether the participant had been given rescue medication. Summary statistics will be provided for incidence of treatment-emergent adverse events (TEAEs), serious adverse events (SAEs), and study discontinuation due to adverse events (AEs) or deaths from the time of first dose through end of safety follow up. Counts and proportions of subjects experiencing AEs will be reported for each treatment group, and Fisher's exact test will be used to compare the treatment groups. For continuous laboratory analytes, summary statistics will be provided by visit, with statistical comparisons among treatment at each visit conducted using a mixed-model for repeated measures (MMRM) analysis. Selected safety analyses may be conducted excluding data after introducing another anti-hyperglycemic therapy (for example, rescue therapy)

Additional details, including analysis of adverse events of special interest, will be provided in the SAP.

2. Schedule of Activities

The Schedule of Activities described below should be followed for all patients enrolled in Study GPHO. However, for those patients whose participation in this study is affected by exceptional circumstances (rare events that may cause disruptions to the conduct of the study, such as pandemics or natural disasters), please refer to Appendix 7 for additional instructions.

Table GPHO.1. Schedule of Activities

	Study Period I		Study Period II																	Study Period III	
	Screening/ Lead in		Treatment Period																	Safety F/U	
Visit	1	2	3 ^a	4	5	6	7	8	9	10	11	12	13	14	15	16	17	18	19	ET ^b	801
Week of Treatment	-3	-2	0	1	2	3	4	5	6	7	8	10	12	14	16	20	24	32	40		4 weeks Post End of Tx
Allowable Deviation (days) ^c	-	±3	±7	±3	±3	±3	±3	±3	±3	±3	±3	±3	±3	±3	±3	±3	±3	±7	±7		±7
Fasting Visit ^d			X				X				X		X		X	X	X		X	X	X
Telephone Visit				X		X		X		X		X		X							
Informed consent	X																				
Randomization			X																		
Clinical Assessments																					
Medical history ^e	X																				
Physical examination	X																		X	X	
Height	X																				
Weight ^f	X		X				X				X		X		X	X	X	X	X	X	X
Waist circumference			X				X				X		X		X	X	X	X	X	X	X
Electrocardiogram			X																X	X	X
Vital signs (2 sitting BP and PR) ^g	X		X		X		X		X		X		X		X	X	X	X	X	X	X

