- ^b Patients who are unable or unwilling to continue in the study for any reason will perform an ET visit. If the patient is discontinuing during an unscheduled visit, that visit should be performed as the ET visit. If the patient is discontinuing during a scheduled visit, that visit should be performed as an ET visit. Visit 801 (safety follow-up visit) should be performed 4 weeks after the ET visit as the final study visit.
- ^c The visit date is determined in relation to the date of the randomization visit (± the allowed visit window).
- ^d On visits 3, 7, 11, 13, 15, 16, 17, 19, ET, and at follow-up, patients should be reminded to report to the site in a fasting condition, after a period of approximately 8 hours without eating, drinking (except water), or any significant physical activity and before taking study drug(s), metformin and sulfonylurea (if used).
- ^e Medical history includes assessment of preexisting conditions (including history of gallbladder disease, cardiovascular disease, and medullary thyroid carcinoma) and substance usage (such as, alcohol and tobacco).

- ^f Weight measurements must be in kilograms.
- ^g Vital sign measurements should be taken before obtaining an ECG tracing and before collection of blood samples for laboratory testing, at visits where required. The participant should sit quietly for 5 minutes before vital sign measurements are taken. For each parameter, 2 measurements will be taken using the same arm; the recordings should be taken at least 1 minute apart. BP must be taken with an automated blood pressure machine.
- ^h Dilated fundoscopic examination will be performed for all patients between Visit 2 and Visit 3, unless there is a contraindication to dilate the eye (ie. closed angle glaucoma). The diagnosis will be made by an eye care professional (ophthalmologist or optometrist) before Visit 3 to exclude patients with proliferative diabetic retinopathy and/or diabetic maculopathy or nonproliferative diabetic retinopathy that requires acute treatment. The results from this examination will be recorded on a specific retinopathy eCRF as a baseline measure of retinopathy. Follow up dilated fundoscopic examination should be performed when clinically indicated, and the results recorded on the retinopathy eCRF.
- ⁱ Includes counseling on diet and exercise, symptoms and management of hypoglycemia, etc.
- ^j All training should be repeated as needed to ensure patient compliance.

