6.1. Populations for Analyses

For purposes of analyses, [Table GPHO.6.1](#) defines the following analysis sets:

Table GPHO.6.1. Analysis Populations/Datasets

Population/Dataset	Description
Screened population	All participants who sign informed consent
Randomized population	All patients who are randomly assigned a treatment arm
Modified intent-to-treat (mITT) population	All randomly assigned participants who are exposed to at least 1 dose of study drug. In the event of a treatment error, participants will be analyzed according to the treatment they were randomized.
Efficacy analysis set (EAS)	Data obtained during Study Period II from the mITT population, excluding data after initiating rescue antihyperglycemic medication or discontinuing study drug (last dose date +7 days).
Full analysis set (FAS)	Data obtained during Study Period II from mITT, regardless of adherence to study drug or initiation of rescue antihyperglycemic medication.
Safety analysis set (SAS)	Data obtained during Study Periods II or III from mITT, regardless of adherence to study drug or initiation of rescue antihyperglycemic medication.
Per Protocol (PP)	Patients included in the randomized population who have completed Week 40 of study treatment without permanent discontinuation of study drug and without significant protocol deviations through Week 40 that would significantly impact the primary objective, excluding data after initiating rescue antihyperglycemic medication. Treatment group will be defined on the basis of the treatment the patients actually receive. Randomized maintenance dose will be used if patients with de-escalation.

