Selected efficacy analyses will also be conducted using the Per-Protocol (PP). PP population will include all patients in the randomized population who completed week 40 of study treatment without permanent discontinuation of study drug and without significant protocol deviations through Week 40 that would significantly impact the primary objective, excluding data after initiating rescue antihyperglycemic medication. Patients in the PP population will be analyzed according to the treatment the patients actually received. Randomized maintenance dose will be used if patients with de-escalation. Those patients who have their dose de-escalated, will not be escalated again. The dose can be de-escalated only once.

Safety assessment will be based on all available data, irrespective of whether they were obtained while the participants had discontinued the study drug or whether the participant had been given rescue medication. Selected safety analysis (e.g., hypoglycemia) will be conducted after excluding data on rescue therapy.

End of study participation for a patient will be the earliest of date of death, date of withdrawal from further participation in the study, or date of safety follow-up visit (Visit 801). For patients considered to be lost-to-follow-up, end of study participation will be the date of lost-to-follow-up reported by the investigator. Patient data included in the database after the last date of study participation (date of early termination or date of safety follow-up) will be excluded from statistical analysis.

Summary statistics for categorical measures (including categorized continuous measures) will include sample size, frequency, and percentages. Summary statistics for continuous measures will include sample size, mean, SD, median, minimum, and maximum. The summary statistics will be presented by nominal visit.

Statistical treatment comparisons will only be performed between tirzepatide doses and insulin glargine. Since the trial is not adequately powered to detect differences among tirzepatide doses, comparisons among tirzepatide arms will not be performed unless otherwise specified.

Statistical summaries and results of statistical analyses will be displayed in the following treatment order: 5 mg tirzepatide, 10 mg tirzepatide, 15 mg tirzepatide, insulin glargine.

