6.13. Safety Analysis

Unless specified otherwise, safety assessments will be based on the SS ([Table GPHO.6.1](#)). All events that occur between the date of first dose of study drug to the date of patient's safety follow-up visit or patient's end of study participation will be included, regardless of the adherence to study drug or initiation of rescue therapy. The events occurring on the day of the first dose of study medication will be counted as post-treatment. For assessing benefit and risk profile through 40-weeks, selected safety analyses will be conducted by utilizing safety data from first dose through the date of 40-week visit. Some safety analyses may be conducted after excluding data after the initiation of new antihyperglycemic therapy. Unless specified otherwise, statistical assessment of homogeneity of the distribution of categorical safety responses among treatment arms will be conducted using Fisher's exact test.

The mean change from baseline difference among treatment at all scheduled visits will be assessed via a MMRM using REML. The model will include country, baseline HbA1c ($\leq 8.5\%$, $> 8.5\%$ [≤ 69 , > 69 mmol/mol]), baseline concomitant oral antihyperglycemic medication, treatment group, visit, and treatment-by-visit interaction as fixed effects, and baseline value of the safety parameter as a covariate. To model the covariance structure within patients, the unstructured covariance matrix will be used. If this model fails to converge, the covariance structures will be tested in order specified in Section 6.12.1.1.

For selected safety parameters, time-to-first-event analysis via the cox-proportional hazards model may be conducted. Patients without the event will be censored at the end of study participation. For patients experiencing the event, the “time-to-first-event” will be the time (in days) from first dose to first occurrence of the event.

Where necessary, the rate of events will be analyzed using a generalized linear mixed-effects model assuming the number of events follow a negative binomial distribution, and with treatment as a fixed effect. The logarithm of days during the active treatment period will be adjusted as an offset to account for possible unequal treatment duration of follow-up between patients.

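### Read literally, SAP 6.2 cuts off safety follow-up after the early-termination visit, against the SAP's own safety analysis set and the protocol

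*SAP*

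**What the plan says.** SAP 6.2 (General Considerations) gives two linked rules. The first is a definition: "End of study participation for a patient will be the earliest of date of death, date of withdrawal from further participation in the study", with Visit 801 as the third alternative. Patients lost to follow-up have a separate rule, the date that the investigator reports. The second is an exclusion: data "after the last date of study participation (date of early termination or date of safety follow-up) will be excluded from statistical analysis".

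The protocol's Schedule of Activities gives patients who cannot or will not continue in the study an ET visit, and its footnote adds that "Visit 801 (safety follow-up visit) should be performed 4 weeks after the ET visit as the final study visit". Protocol 8.2 repeats this, and SAP 5.1 also makes the safety follow-up visit the last one for ET patients.

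On which safety data count:

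- SAP 6.1 defines the safety analysis set as "Data obtained during Study Periods II or III from mITT, regardless of adherence to study drug or initiation of rescue antihyperglycemic medication". Period III is the safety follow-up.
- SAP 6.2 itself says: "Safety assessment will be based on all available data, irrespective of whether they were obtained while the participants had discontinued the study drug".
- The protocol synopsis says: "Safety assessment will be based on all available data including 4-week safety follow up period".
- SAP 6.13 counts events from first dose up to the date of the patient's "safety follow-up visit or patient's end of study participation will be included", and censors event-free patients in time-to-first-event analyses at the end of study participation.

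**The concern.** Early termination is a named visit in this trial, and it comes about four weeks before the last planned visit. If the ET date is the last date of participation, the exclusion removes data that the protocol plans to collect and says it will use. Completers keep their four weeks of follow-up; early terminators lose theirs.

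Visit 801 collects adverse events, hypoglycemic events, ECG, chemistry, calcitonin, pancreatic enzymes, anti-drug antibodies (ADA) and the matching PK sample. Protocol 9.4.4 gives the Visit 801 antibody sample a specific purpose, immunogenicity after washout of tirzepatide. Under the literal rule, early terminators lose that sample and their post-treatment calcitonin value. A new event or death between the ET visit and Visit 801 could be absent from the TEAE and SAE summaries and from time-to-event analyses. The loss follows withdrawal, so it can differ between arms if withdrawal does.

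**Working it through.** The plan states no figure on this point, so there is none to reproduce. The check is a comparison of the rules, followed by an illustrative size.

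**1. Apply SAP 6.2 to an early terminator who attends Visit 801.** The candidate end dates are the withdrawal date and, about four weeks later, Visit 801. The definition takes the earlier. If withdrawal is dated at the ET visit, participation ends there. The bracket in the exclusion sentence names the ET date explicitly. Everything later, including Visit 801, is then excluded from statistical analysis.

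**2. Compare with the other rules for the same patient.**

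| Source | Data between ET and Visit 801 |
|---|---|
| SAP 6.2, definition and exclusion, literal reading | Out |
| SAP 6.2, data basis for safety | In |
| SAP 6.1, safety analysis set | In |
| SAP 5.1, final visit of ET patients | Visit 801 is part of participation |
| Protocol synopsis, safety analysis | In |
| SAP 6.13, event window | Undetermined: two end dates joined by *or* |
| SAP 6.13, censoring | End of participation, so the ET date under the literal reading |
| SAP 6.10, duration of follow-up | Runs to the safety follow-up visit |

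Two inconsistencies follow. Under SAP 6.13, events could be counted to Visit 801 while event-free patients are censored at ET. Under SAP 6.10, reported follow-up would include four weeks whose data SAP 6.2 excludes.

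**3. Who is affected.** Only patients who leave the study early and still provide data after the ET visit. Patients who stop only study drug stay in the trial (Protocol 8.1.1). Patients who refuse all further contact have no planned Visit 801 data to lose (Protocol 8.2).

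**4. Illustrative size.** Inputs: 956 patients; 40 weeks of treatment plus 4 of follow-up; 28 days from ET to Visit 801. Assumptions: 2% to 15% of patients withdraw early, and all of them attend Visit 801. The 25% in the sample-size section covers rescue or stopping treatment, not leaving the study, so it cannot serve as the rate.

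- Planned follow-up: 956 × 44 × 7 = 294,448 patient-days.
- At 2%: 956 × 0.02 ≈ 19 patients; 19 × 28 = 532 days; 532 / 365.25 ≈ 1.5 patient-years; 532 / 294,448 ≈ 0.2%.
- At 15%: 956 × 0.15 ≈ 143 patients; 143 × 28 = 4,004 days; 4,004 / 365.25 ≈ 11 patient-years; 4,004 / 294,448 ≈ 1.4%.

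For an individual the share is larger. A patient who leaves at Week 8 loses 28 / (56 + 28) = 33% of observed days; one who leaves at Week 20 loses 28 / (140 + 28) = 17%.

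**The case against.** The best defence is that the bracket offers alternatives: the ET date for a patient with no Visit 801, and the Visit 801 date for a patient who has one. No passage equates withdrawal from further participation with the ET visit, and a patient still due at Visit 801 has arguably not withdrawn. SAP 5.1, the safety analysis set and the all-available-data sentence fit that reading. This shows that the intent was probably benign. It does not remove the defect: when a withdrawal date and a later Visit 801 both exist, the definition selects the earlier, and SAP 6.13 does not say which of its two dates governs.

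Other limits stand in full:

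- A reader might infer that a death after the ET visit would disappear. It would not. SAP 6.13.1.1 lists all deaths, SAP 6.13.1.2 lists all SAEs, and SAP 6.13.1 plans narratives for both. The summary counts and time-to-event analyses are what is exposed.
- A reader might infer that every early withdrawer loses a mandatory visit. Visit 801 is worded as required for treatment completers; ET patients are asked to attend, and some will have no post-ET data.
- Calcitonin, chemistry, pancreatic enzymes, ADA, PK and ECG are also taken at the ET visit. Only the later repeat is lost.
- Under Protocol 8.2, stopping drug because of an adverse event is not a valid reason to leave the study. This weakens the argument that the loss falls on patients with adverse events, although SAP 6.13.1.3 expects some to leave the study for that reason.

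**Conclusion.** The point holds as a conflict in the stated rules. Applied literally, SAP 6.2 drops the post-ET safety data of early terminators who provide them, against SAP 5.1, SAP 6.1, another sentence of SAP 6.2 and the protocol synopsis. The stronger conclusion, that these data will certainly be left out, is not supported, because the bracket has a second plausible reading.

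The overall loss is probably small: about 0.2% to 1.4% of planned follow-up. That rests on an assumed 2% to 15% withdrawal rate with full attendance at Visit 801; lower attendance means less to lose. The loss matters more than its size suggests because it is tied to withdrawal and includes the washout samples. The primary and key secondary efficacy analyses use Period II data and are not touched. It should be corrected because the correction is cheap and the cut-off governs the safety tables, but it does not threaten the trial's main conclusions.

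**What to change.** In SAP 6.2, define end of study participation in this order:

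1. the date of death, if the patient dies on or before Visit 801 (or its planned date, if the visit was not performed);
2. otherwise the Visit 801 date when that visit is performed, including after an ET visit;
3. otherwise the ET or withdrawal date.

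Keep the existing rule for patients lost to follow-up. Change the bracket in the exclusion sentence to match. In SAP 6.13, replace the two alternative end dates with this single date, and use it for both event inclusion and censoring.

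The cost is a few lines of SAP text and one derived date. No new data are needed. It should be settled before database lock, since a cut-off chosen afterwards would be a post hoc decision about safety data.
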